Made of administration			
Mode of administration	I ranscutaneous - adheres to chest wall		
Comparator product(s)	Not applicable		
Duration of assessment	12 weeks		
Statistical methods	Descriptive statistics will be presented for all primary and secondary		
	endpoints. Additionally, CC/hour will be log transformed and		
	summarized in terms of geometric mean and 95% confidence		
	intervals.		

Page 4 of 71

Proprietary confidential information © 2022 Boehringer Ingelheim International GmbH or one or more of its affiliated companies

FLOW CHART

Study Periods	Screening*	Baseline* Visit	Remote Study Visits				EoS Visit
Visit	1	2	3	4	5	6	7/EoS
Days	- 1 wk	1	3	28	56	82	84
Time window for visits			+ 2 days	$\pm 5 \text{ days}$	$\pm 5 \text{ days}$	- 2 days	$\pm 5 \text{ days}$
Informed consent	Х						
Review of in-/exclusion criteria	Х						
Demographics	Х						
Smoking Status/history	Х						
Medical history (Comorbidities)	Х						
Pregnancy status (where available)	Х						Х
COVID-19 history (including vaccination status)	Х						
Non IPF Pulmonary Fibrosis (including ILD diagnosis category) or IPF	Х						
Progressive Pulmonary Fibrosis Phenotype (Y/N)	Х						
Concomitant therapy (including prescription medications for Pulmonary Fibrosis)		Х		Х	Х		Х
Historical Pulmonary Function Tests (FVC & DLCO) ²	Х						
Historical HRCT Pattern ³ (UIP, Probable UIP, Indeterminate for UIP, Inconsistent w/UIP)	Х						
Physical examination		Х					Х
Vital signs ⁴		Х					Х
SpO ₂		Х					Х
In-Office Spirometry ⁵		Х					Х
Distribute & provide instruction on cough monitor		Х					
Distribute & provide instruction on home spirometer		Х					
Home Spirometry			X ^{7,9}	Х	Х	X ^{7,9}	
Reporting of AEs/SAEs ¹⁰ & Unscheduled clinical visits		Х		Х	Х		Х
Videoconference remote visit				Х	Х		
24-hour cough monitor recording ¹¹		Х		X ¹¹	X ¹¹	X ¹¹	
24-hour cough monitor data upload ¹²		Х		Х	Х	Х	
Remote Procedures Compliance Check 13							
(Home spirometry, Videoconference remote visit (V4, V5), Cough recordings)			Х	Х	Х	Х	
Return of cough monitor & home spirometer							Х
Patient survey regarding use of cough monitor and home spirometer							Х

Boehringer Ingelheim BI Study No.: 1490-0005 c39406431-01

Protocol

Proprietary confidential information © 2022 Boehringer Ingelheim International GmbH or one or more of its affiliated companies

Study Periods	Screening*	Baseline* Visit	Remote Study Visits			EoS Visit	
Visit	1	2	3	4	5	6	7/EoS
Days	- 1 wk	1	3	28	56	82	84

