Completion of patient participation							х

*Screening and Baseline Visit can occur on the same day.

- Most proximate historical FVC & DLCO within 6 months and most distant FVC & DLCO within 12 months should be recorded
- 3) Most proximate historical HRCT performed within the previous 12 months
- 4) Measurements of vital signs should precede blood sampling
- 5) Site personnel should confirm that FVC continues to meet eligibility criteria for study inclusion prior to preceding with additional study procedures
- Patients will need to complete home spirometry within 72 hours, but not on the same day as Visit 2/Baseline study visit.
- 8) Patients will need to complete home spirometry in the 72 hrs preceding the day of Visit 7/EoS
- 9) Efforts should be made to perform spirometric measurements at approximately the same time of the day, at least within the same half-day (morning vs afternoon).
- 10) As described in Section 5.2.6.1.1
- 11) 24-hour cough recording should be initiated immediately following the end of the remote visit.
- 12) 24-hour cough recording data upload should occur immediately after completion of 24-hour CC recording. Patients should place the biosensor on the charger next to the study provisioned mobile phone to allow for data to upload.
- 13) Study personnel conducting the visit will review whether the intended procedures for the visit have been completed. If not, the study team will inquire as to whether the patient requires assistance with any specific aspects of the visit. Site staff will receive notification via email each time a patient completes a cough count recording with successful data upload. If the site does not receive this type of notification, the site should contact the patient to assess whether the patient requires assistance with any elements of the 24 hour cough recording and upload.

 P4U6451-U1
 Protocol
 Page 6 of 71

 Proprietary confidential information © 2022 Boehringer Ingelheim International GmbH or one or more of its affiliated companies

TABLE OF CONTENTS

TITLE PA	AGE	1
PROTOC	OL SYNOPSIS	2
FLOW CI	HART	4
TABLE O	PF CONTENTS	6
ABBREV	IATIONS AND DEFINITIONS	9
1.	INTRODUCTION	.12
1.1	MEDICAL BACKGROUND	.12
1.2	DEVICE PROFILE	.13
1.3	RATIONALE FOR PERFORMING THE STUDY	.14
1.4	BENEFIT - RISK ASSESSMENT	.14
1.4.1	Benefits	.14
1.4.2	Risks	.15
1.4.3	Discussion	.15
2.	STUDY OBJECTIVES AND ENDPOINTS	.16
2.1	MAIN OBJECTIVES, PRIMARY AND SECONDARY ENDPOINTS	.16
2.1.1	Main objectives	.16
2.1.2	Primary endpoint(s)	.16

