If a patient misses a visit, the site is asked to alert the contracting entity to determine if the visit should be rescheduled. Subjects are free to discontinue or withdraw from the study at any time. Reason for discontinuation or withdrawal will be collected; however, reasons for withdrawal of consent do not have to be disclosed. Unless otherwise requested by the participant, all data obtained up to consent withdrawal will be retained in the database.

Screening Period (Visit 1)

- Following provision of informed consent, Inclusion & Exclusion criteria should be reviewed as per the FC
- During the screening visit, demographic information will be collected.
 - Age on the day of informed consent (in years)

- Sex (male, female; to describe the patient's sex at birth)
- Ethnicity and race in order to sufficiently characterize the patient population, to support possible subgroup analyses if needed unless not acceptable according to local regulations.
- Medical history (Comorbidities, COVID-19 infection history and vaccination status)
- Pregnancy status (where available)
- Non IPF pulmonary fibrosis (including ILD diagnosis category) or IPF Diagnosis
- Presence or absence of progressive pulmonary fibrosis (PPF) phenotype
- Smoking status/history
- Concomitant medications
- HRCT pattern (most recent study within previous 12 months)
- FVC & DLCO (most recent value within 6 months prior to V2 & most distant value within 12 months of V2)

Visit 2/Baseline Visit – On site

The Screening Visit and Baseline Visit can occur on the same day.

Vital signs will be taken, and a physical exam performed. Subsequently, a pulmonary function test will be performed to measure FVC.

Instructions for utilizing and storing the cough monitor will be reviewed. The patient will place the biosensor onto their chest wall with supervision and assistance (as needed) from the study team. The sensor will be set and started on recording mode for the planned 24hrs. recording. At completion of 24hrs. of recording the next day, the patient will place the charger to allow for data upload via Bluetooth connected app on the study-provided mobile phone. The sensor will be charged for the next visit and stored as per vendor instructions until the next recording at Visit 4. At Visit 2, patients will additionally receive a home spirometer and instructions for use will be reviewed with the patient including access to the video assist portal on the provisioned mobile phone for study use.

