Subsequently, interval history will be obtained, followed by video-assisted supervised home spirometry with the site study team. Immediately following the end of the study visit, the patient will initiate a 24-hour cough count recording. At completion of 24 hrs. of recording the next day, the patient will remove the sensor from their chest wall and place the sensor onto a charger to allow for data upload via Bluetooth connected app on the study-provided mobile phone. The charger will be placed next to the study provided mobile phone, which is "pre-loaded" with the place app, to allow for data upload. The sensor will be charged for the next visit and stored as per vendor instructions until the next recording at Visit 6. The site study team will confirm that the prior 24-hour cough recording was completed and offer to assist the patients with any part of the 24-hour cough recording that they were having trouble with.

Visit 6- Remote

Visit 6 will occur on the 82nd day (-2 days) prior to the EoS visit. On the day of the study visit, the patient is asked to complete home spirometry (Visit 6) via logon to the platform for video supervision by a spirometry trained member of the site study team. Immediately following the end of the study visit, the patient will initiate a 24-hour cough recording. At completion of 24 hrs. of recording the next day, the patient will remove the sensor from their chest wall and place the sensor onto a charger to allow for data upload via Bluetooth connected app on the study-provided mobile phone. The charger will be placed next to the study provided mobile phone, which is "pre-loaded" with the provided app,

Proprietary confidential information © 2022 Boehringer Ingelheim International GmbH or one or more of its affiliated companies

to allow for data upload. Once data upload is complete, the sensor and study provided phone will be stored for return to the site at the EoS visit (Visit 7).

Visit 7 – On site

The End of Study Visit (EoS/V7) will occur on the 84th day (+/- 5 days) following study enrollment/baseline visit.

Interval history will

be obtained; vital signs and a physical exam will be performed. Participants will then undergo spirometry on-site.

The and home spirometry devices will be returned to the site as will the provisioned mobile phone.

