6.7 BASELINE, TIME WINDOWS AND CALCULATED VISITS

In general baseline is defined as measurements collected at the Baseline visit. For the first of the value at the Baseline visit is missing the value at the Screening visit will be used.

As this is a low-interventional trial without treatment or other intervention for cough, in cases where the first cough recording or in-office spirometry occurred after the Baseline visit (Visit 2) then the start date of the first cough recoding or first in-office spirometry visit will be considered the Baseline measurement and the time windows below will be applied to the subsequent visits using the respective baseline date as day 1.

Table 6.7: 1Time windows for assignment of visits for	statistical analysis
---	----------------------

		Time windows (days)			
		Planned day	Window		
Visit			(relative to		
name	Visit label		planned day)	Start (inclusive)	End (inclusive)
V1	Screening	-7	n/a		
V2	Baseline	1	n/a	-7	1
V3	Day 3 ^a	3	-1/+13	2	16
V4	Week 4 ^a	29	-12/[contact]
V5	Week 8 ^a	57	-13/[contact]
V6	Day 82 ^a	83	-13/na	71	One day before
	-				last visit (in-
					office)
V7	Week 12/EoS	85	na/na	Date of last visit (in-	Last visit date
				office)	recorded

^a Remote visit

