The % of analysable data per 24-hour recording period will be derived from the cough count recording times(Total readable recording time) and defined as:

Total readable recording time

24 (hours)

- x 100

Descriptive statistics will be produced by visit as well as the number and percentage of patients who have $\geq 80\%$ (19.2 hrs) of analyzable data.

• Feasibility of hybrid study design (successful completion of all elements of remote visit)

Successful completion of a remote visit will be based on the questions on the home study procedures eCRF:

- Was home spirometry performed? (Visit 3, Visit 4, Visit 5, Visit 6)
- Was the videoconference televisit completed? (Visit 4, Visit 5)
- Was the 24 hour cough recording completed? (Visit 3, Visit 4, Visit 5)

The number and percentage of patients who complete each element will be tabulated by visit as well as the number an percentage of patients who complete all elements by visit.

Correlation analyses:

Sample Spearman and Pearson correlation coefficients for the pairs of CC/hr and FVC measurements listed above along with the associated p-values to assess the relationship between objective cough frequency and FVC (mL), correlations will be calculated. Scatter plots for the pairs of variables will also be produced.

Boehringer Ingelheim

 TSAP for BI Trial No: 1490-0005
 Page 19 of 27

 Proprietary confidential information © 2024 Boehringer Ingelheim International GmbH or one or more of its affiliated companies

001-MCS-50-415_RD-01 (3.0) / Saved on 18 Jan 2021

Boehringer Ingelheim TSAP for BI Trial No: 1490-0005

Proprietary confidential information © 2024 Boehringer Ingelheim International GmbH or one or more of its affiliated companies

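### SAP 6.7 sets no latest day for a substitute baseline: a late first cough recording empties Week 12, and in a rare case one FVC value can serve as both Baseline and Week 12

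*SAP*

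**What the plan says.** SAP 6.7 takes baseline from the Baseline visit. If the first cough recording or first in-office spirometry came later, "the start date of the first cough recoding or first in-office spirometry visit will be considered the Baseline measurement". Visits subsequent to that date are then assigned with the windows of Table 6.7: 1, counting the substitute date as day 1, separately for cough and for FVC. The rule gives no latest day.

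In Table 6.7: 1 the Baseline row runs from day -7 to day 1. The Day 82 row (Visit 6, which supplies the Week 12 cough recording) opens on day 71. The Week 12/EoS row (Visit 7) is defined only by the date of the last in-office visit, with no minimum day.

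The Flow Chart marks "In-Office Spirometry" at Visits 2 and 7 only. Protocol 6.1 agrees: at Visit 2, "Subsequently, a pulmonary function test will be performed to measure FVC"; at Visit 7, "Participants will then undergo spirometry on-site". Spirometry at Visits 3 to 6 is home spirometry, so it cannot supply an in-office baseline.

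For the percentage of analysable data, SAP 7.5.2 states: "Descriptive statistics will be produced by visit as well as the number and percentage of patients who have" at least 80% (19.2 hours). SAP 6.6 defines one approach that ignores the 6.7 windows (original results) and one that applies them (observed cases). The readable SAP text does not say which applies to this table.

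**The concern.** The SAP's reason for the substitution is that no treatment is given, so a baseline taken a little late is still a fair baseline. That supports a delay of days, not of weeks or of the whole study. The Baseline row does not act as a cap, because day 1 itself moves to the substitute date.

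Three outputs are exposed:

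- **FVC at baseline and its change at Week 12.** An end-of-study value could be reported as baseline, and possibly as Week 12 as well. It would also enter the correlations between cough and FVC.
- **Cough counts by visit.** A late first recording moves all later recordings into earlier columns, and the patient has no Week 12 value for the primary endpoint although Visit 6 was recorded.
- **Feasibility of remote cough capture.** A first-use failure could show as a loss at the end of the study. That would mislead a pilot meant to inform the design of later trials.

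**Working it through.** **Inputs**

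- Planned SAP days are 1, 29, 57, 83 and 85 for Visits 2, 4, 5, 6 and 7 (Table 6.7: 1). The Flow Chart's days 28, 56, 82 and 84 are each one lower.
- Flow Chart tolerances are ±5 days for Visits 4 and 5 and -2 days for Visit 6. On the SAP scale these give days 24-34, 52-62 and 81-83.
- Window starts: Visit 3, 3 - 1 = 2 (end 3 + 13 = 16, as stated); Week 4, 29 - 12 = 17; Week 8, 57 - 13 = 44; Visit 6, stated as 71.
- Assumption: the Week 4 and Week 8 end days are not legible in the text available, so I take the day before the next window opens, 43 and 70.
- The Visit 6 offset gives 83 - 13 = 70, not the stated 71. I use 71. With 70, the limits in step 3 move by one day and nothing else changes.
- n = 50 (Protocol 7.5).

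Rebasing formula: new day = old day - substitute day + 1.

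**1. FVC, first in-office test at Visit 7.** New day = 85 - 85 + 1 = 1, so the value is Baseline. The same date is also the last in-office visit, which is all that the Week 12/EoS row requires.

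- Reading A, the row applies: Baseline and Week 12 are one value, and the change is exactly 0 mL.
- Reading B, the windows apply only to visits after the substitute: Week 12 and the change are missing. The reported baseline FVC was measured 85 - 1 = 84 days after Visit 2.

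Under reading A, k such patients multiply the mean change by (50 - k)/50: 0.98 for k = 1, 0.96 for k = 2, 0.94 for k = 3. The documents give neither k nor an expected change. With an assumed mean of -50 mL (range -25 to -100) and k = 3, the result is -47 mL (-23.5 to -94).

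**2. Cough, first recording at Visit 4 (day 29).** Visit 5: 57 - 29 + 1 = 29, labelled Week 4. Visit 6: 83 - 29 + 1 = 55, labelled Week 8. Nothing reaches day 71, so Week 12 is empty.

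At the extremes of the tolerances, Visit 5 falls between 52 - 34 + 1 = 19 and 62 - 24 + 1 = 39, always in Week 4. Visit 6 falls between 81 - 34 + 1 = 48 and 83 - 24 + 1 = 60, always in Week 8. If the first recording is at Visit 5 (day 57), Visit 6 becomes 83 - 57 + 1 = 27 (Week 4), and both later columns are empty.

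**3. How late a substitute can be if rebasing is kept.** For Visit 6 to stay in its window, 83 - s + 1 ≥ 71, so s ≤ 13. For a Visit 6 on day 81, s ≤ 11. A substitute on Day 16 puts a day-83 recording on 83 - 16 + 1 = 68, too early for Week 12, and puts Visit 4 on 29 - 16 + 1 = 14, inside the Visit 3 window.

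**4. Feasibility.** The threshold reproduces: 0.80 × 24 = 19.2 hours. For illustration only, assume that 5 of 50 Visit 2 recordings fail completely, none is repeated before Visit 4, and all later recordings reach 80%. SAP 7 by default keeps patients with missing values in the denominator.

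| Column | Nominal visits | 6.7 windows, failed attempt not counted |
|---|---|---|
| Baseline | 45/50 = 90% | 50/50 = 100% |
| Week 12 | 50/50 = 100% | 45/50 = 90% |

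With 3 failures the figures are 94% and 100%, shown as 100% and 94%.

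**The case against.** The case against is substantial, and much of it stands.

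- **A reader might infer that false zero changes will enter the FVC endpoint.** The documents do not establish that. SAP 6.7 applies its windows to *subsequent* visits, and a Visit 7 test is not subsequent to itself, so reading B is at least as natural. It removes the zero but still reports an end-of-study value as baseline.
- **The FVC case should be rare.** FVC at the baseline visit is an inclusion criterion, and a Flow Chart footnote adds: "Site personnel should confirm that FVC continues to meet eligibility criteria for study inclusion prior to preceding with additional study procedures". The case needs a patient with no in-office test at Visit 2, or at any unscheduled visit before Visit 7, who nevertheless stays in. Against that, SAP 6.7 itself foresees a late first spirometry, and SAP 6.3 states no exclusion from the Entered Set. Deviation handling sits in specifications outside the SAP.
- **A reader might infer that a failed first recording vanishes from the feasibility results.** That needs two things the SAP leaves open: that a recording started under supervision at Visit 2 and then lost did not occur, and that the table uses the 6.7 windows. A partly readable recording stays in the baseline column. The remote-visit table asks about the cough recording at Visit 3, where the Flow Chart has a compliance check but no recording, so that item may capture the Visit 2 attempt. Even when relabelled, the loss reappears as a missing Week 12 entry.
- **Sites contact the patient when no upload notice arrives** (Protocol 4.3), so a repeat within days is more likely than a wait until Visit 4.
- **One value filling two visits cannot happen for cough**, because the Visit 6 window opens on day 71.

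None of this supplies a latest day, and the relabelling in step 2 does not depend on any of these readings.

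**Conclusion.** The point holds as a minor gap in a stated rule. The firm part is that SAP 6.7 has no latest day, and a first cough recording at Visit 4 always turns Visits 5 and 6 into Weeks 4 and 8 and leaves Week 12 empty. That rests on Table 6.7: 1 and the inferred window ends.

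The FVC part is conditional. The text permits a change of exactly 0, or else an end-of-study value labelled as baseline, in a patient who should seldom exist. Each such patient under reading A pulls the mean change toward zero by 1/50, or 2%.

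The feasibility part is an ambiguity, not a demonstrated error. The 100%/90% reversal shows what the wording allows; its counts are assumed and are not a forecast. No hypothesis test depends on any of this.

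**What to change.** Add three rules to the SAP:

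1. No measurement may serve two analysis visits, and a Visit 7 spirometry may not be Baseline.
2. Accept a substitute baseline only before the Week 4 window opens (by Day 16 counted from Visit 2), and keep later windows anchored to Visit 2. If rebasing is kept instead, cap the substitute at about Day 11-13, so that a Visit 6 recording on day 81-83 stays in its window. Beyond the cap, set baseline and change to missing and report the value under its own visit.
3. Tabulate the feasibility endpoints of 7.5.2 by nominal protocol visit, without the 6.7 substitution, and count a failed or absent recording as 0% analysable.

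The cost is SAP wording only; no new data are needed. A few patients may lose a change-from-baseline value. With windows anchored to Visit 2, late starters have a shorter interval: at the Day 16 limit, 83 - 16 = 67 days to Visit 6 instead of 83 - 1 = 82.

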1.3 RATIONALE FOR PERFORMING THE STUDY

As highlighted, significant gaps in knowledge remain regarding etiology of cough, consequences of cough and appropriate treatment of cough in patients with pulmonary fibrosis. A further understanding of the similarities and differences in cough among persons with Non IPF Pulmonary Fibrosis and IPF, together with insight into the pattern and impact of cough in these patients is required.

The current pilot aims to assess cough frequency, indirect measures of cough intensity and the association between objective cough measures and lung physiology, a host of patient-reported outcomes and blood-based biomarkers in a patient cohort with Non IPF Pulmonary Fibrosis or IPF. This study aims to expand the understanding of the disease and its symptoms, thereby narrowing the existing gap in knowledge, and to help support the development of future compounds targeting cough.

We will utilize a hybrid study design in which 4 visits will be conducted remotely and all cough data will be captured via a wearable, digitally enabled cough monitor with bluetooth capabilities that allow secure remote upload. Furthermore, patients will perform video-assisted home spirometry. The intention of incorporating 4 remote visits into the study design is to assess the potential to ease the burden of study procedures on patients and physicians, thereby broadening the subject pool to those who might otherwise not have access to enroll in this pilot. If successful, this type of study design could also be employed in Phase 2 and 3 interventional trials and allow a broader and more racially, geographically, and socioeconomically diverse patient population access to clinical trials.

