3.3.4 Discontinuation of patients from assessments

Patients may discontinue study participation or withdraw consent to study participation at any time ("withdrawal of consent"). If the patients agree, they should stay in the study. Even if continuing to wear the cough monitor is not possible, they should attend further study visits to collect important study data.

An individual patient will discontinue the study if:

- The patient has repeatedly shown to be non-compliant with important study procedures and, in the opinion of both, the investigator and contracting entity representative, is not willing or able to adhere to the study requirements in the future.
- The patient can no longer perform the study procedures for medical reasons

Measures to control the withdrawal rate include careful patient selection, appropriate explanation of the study requirements and procedures prior to study enrolment, as well as the explanation of the consequences of withdrawal.

The decision to discontinue or withdraw consent to study participation and the reason must be documented in the patient files and CRF.

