4. CHANGES IN THE PLANNED ANALYSIS OF THE STUDY

For the endpoint "Cough frequency and number of cough bouts at each of the activity levels (exertion): stationary/low, medium/high", activity levels will be categorized as:

- Low activity
- Medium activity
- High activity

"Stationary" activity represents non-wear time.

Only inspiratory crackles will be summarized for the endpoint "Lung sound events (potentially including, but not limited to, inspiratory crackles)

5. **ENDPOINTS(S)**

5.1 **PRIMARY ENDPOINT(S)**

The primary endpoints as stated in the CTP are: Cough count per hour (CC/hr) measured over a 24-hour period at baseline visit, Week 4(V4), Week 8(V5), Week 12 (V6).

Note that these endpoints are the average CC/hour at each of the 4 visits.

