6.6 HANDLING OF MISSING DATA AND OUTLIERS

The following approaches will be applied in this trial:

- The original results (OR) approach implies the presentation of data exactly as observed (not using time windows as described in Section 6.7 and not setting values to missing). OR analysis will be performed on parameters and endpoints for which it is not meaningful to apply any imputation rule for the replacement of missing values.
- Observed cases (OC) approach will include all collected data, without imputation for any missing data after applying the time windows as described in Section 6.7

Missing or incomplete AE dates are imputed according to BI standards.

Other partial start and stop dates, for example, concomitant medications, non-drug therapies, and IPF diagnoses will be imputed to enable subsequent calculation (but not for display) by the following approach:

- If the day of the end date is missing, then the end date is set to last day of the month (or to the patient's end of study participation from End of Study eCRF. if it is earlier than the last day of the month).
- If the day and month of the end date are missing then the end date is set to 31st of December of the year (or to the patient's end of study participation from End of Study eCRF, if it is earlier than the 31st of December of the year).

Boehringer Ingelheim TSAP for BI Trial No: 1490-0005

Proprietary confidential information © 2024 Boehringer Ingelheim International GmbH or one or more of its affiliated companies

- If the day of the start date is missing the start date is set to first day of the month.
- If the day and month of the start date are missing then the start date is set to 1st January of the year.
- All other cases need to be assessed by the trial team on an individual basis, using the above points as guidance.

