7.5.1.1 Primary analysis of the key secondary endpoint(s)

This section is not applicable as no key secondary endpoint has been specified in the protocol.

7.5.2 (Other) Secondary endpoint(s)

CTP Section 7.2.3.1: Secondary endpoints will be summarized descriptively by visit.

Change from baseline in CC/hr at Week 4, Week 8, and Week 12 will be summarized in terms of absolute changes in CC/hr and in terms of geometric mean ratios. Model based estimates for changes from baseline at Week 12, for example least squares means adjusted for baseline CC/hr or other covariates, may be calculated.

Standard descriptive statistical parameters will be tabulated for all other secondary endpoints.

To assess the relationship between objective cough frequency and FVC (mL), correlations (spearman and Pearson) will be calculated between the following variables:

- Baseline CC/hr (log-transformed) and Baseline FVC (mL)
- Baseline CC/hr (log-transformed) and FVC (mL) at Week 12
- Baseline CC/hr (log-transformed) and change from baseline FVC (mL) at Week 12
- CC/hr at Week 12 (log-transformed) and FVC (mL) at Week 12
- Change in CC/hr at Week 12 (calculated from log-transformed values) and change from baseline in FVC (mL) at Week 12

Graphical presentations of the secondary endpoints and correlations may also be produced.

Changes from baseline in CC/hr (absolute changes on the original scale and geometric mean ratios calculated from the log transformed values) at each visit will be presented along with the primary endpoints in the descriptive tabulations. Additionally, geometric mean ratios at Weeks 4, 8 and 12, and 95% CIs will be calculated using a statistical model adjusting for the baseline CC/hr. This model can be described as follows:

$$y_{ij} = \mu + v_j + b_i + e_{ij},$$

where

- $\mathbf{y_{ij}}$ Log(CC/hr at Visit j) Log(baseline CC/hr) for patient i,
- μ overall intercept,
- v_i jth Visit (e.g. Week 4, Week 8, Week 12)
- b_i Log(baseline CC/hr) for subject i,
- e_{ii} the random error associated with subject i at visit j.

The adjusted means, standard errors, lower and upper 95% confidence limits from the above model will then be back-transformed and presented as the geometric mean ratios, geometric standard errors and 95% confidence limits.

Study feasibility endpoints:

• Feasibility of remote cough data capture (defined as % of analysable data per 24-hour recording)

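### SAP Table 6.7: 1 ties both Week 12 windows to the last in-office visit, so an early last clinic visit counts as Week 12 FVC and a V6 cough recording with no later clinic visit falls outside V6

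*SAP*

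**What the plan says.** SAP 5.1 takes the primary endpoint from the protocol: "Cough count per hour (CC/hr) measured over a 24-hour period at baseline visit, Week 4(V4), Week 8(V5), Week 12 (V6"). Week 12 cough is therefore the V6 recording. Week 12 FVC is the in-office measurement at V7, which Protocol 5.1 identifies with Week 12.

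SAP 6.7, Table 6.7: 1, assigns data to these visits as follows:

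- **V6** (planned day 83, offset -13/na) starts on Day 71 and ends "One day before" the last in-office visit.
- **V7, Week 12/EoS** (planned day 85, offset na/na) has a start cell that begins "Date of last visit (in" and refers to the in-office visit. It ends on the last recorded visit date.

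The windows matter under one of the two approaches in SAP 6.6: "Observed cases (OC) approach will include all collected data, without imputation for any missing data after applying the time windows" of Section 6.7. The other approach, original results, ignores them.

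Protocol 6.1 does limit V7: "The End of Study Visit (EoS/V7) will occur on the 84th day (+/- 5 days) following study enrollment/baseline visit". The table does not carry that limit over. Protocol 3.3.4 foresees early stopping: "Patients may discontinue study participation or withdraw consent to study participation at any time". Protocol 6.1 also provides for missed visits and, under disruptive circumstances, for virtual ones.

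**The concern.** The V7 row merges a time point (Week 12) with an event (the last clinic visit). Two consequences follow.

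**FVC.** If the last in-office visit with spirometry comes early, its value is labelled Week 12. It then enters the Week 12 FVC summary, the change from baseline, and correlations such as "Baseline CC/hr (log-transformed) and change from baseline FVC (mL) at Week 12" (SAP 7.5.2). Protocol 7.3 rules out imputation, yet this rule places a shorter follow-up under the Week 12 label.

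**Cough.** The end of the V6 window depends on a clinic visit that has nothing to do with the recording. A patient who completes the V6 recording at home but never attends a later clinic visit has a recording outside V6. The Week 12 primary value, the Week 12 change and the Week 12 term of the baseline-adjusted model may all lose it. That sits badly with a design in which "all cough data will be captured via a wearable, digitally enabled cough monitor" and uploaded remotely.

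**Working it through.** **Inputs.** The V6 and V7 rows of SAP Table 6.7: 1; Protocol 6.1 (V6 on Day 82, minus 2 days; V7 on Day 84, plus or minus 5 days); n = 50 (Protocol 7.5). Let L be the day of the last in-office visit and D the last recorded visit day. The table then gives V6 = [71, L-1] and V7 = [L, D].

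**Step 1: reproduce the table's days.** V3: 3-1 = 2 and 3+13 = 16, both as printed. V6: 83-13 = 70, but 71 is printed (83-12 = 71). Only a Day 70 recording would be affected.

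**Step 2: patients on schedule.** V6 on Days 80 to 82 and V7 on Days 79 to 89 give 3 x 11 = 33 day pairs. V6 precedes V7 in 9+8+7 = 24 of them, which is the order the protocol intends. In all 24 the recording lies in [71, L-1]. Counting days after baseline (81 to 83 and 80 to 90) gives the same 24. Nothing changes for these patients.

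**Step 3: off-schedule cases, rule applied literally.**

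| Case | V6 window | V7 window |
|---|---|---|
| L = 85, recording on Day 83 | [71, 84], contains it | [85, 85] |
| L = 40 | [71, 39], empty | [40, 40], labelled Week 12 |
| L = 120 | [71, 119] | [120, 120], labelled Week 12 |
| Only clinic visit is V2 (L = 1), recording on Day 83 | [71, 0], empty | [1, D] |

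In the last case, if last visit is taken to mean the absent V7, the end of V6 is undefined. If the row is read literally and D = 83, the recording falls in V7, where the protocol's flow chart schedules no cough recording.

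**Step 4: which correlations an early FVC reaches.** Four of the five pairs in SAP 7.5.2 use Week 12 FVC or its change. Two pair it with baseline cough and would receive the Day 40 value. The other two need Week 12 cough, whose window is then empty.

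**Step 5: size, FVC.** Planned interval: 85-1 = 84 days. Share covered = (L-1)/84:

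- Day 29: 28/84 = 33.3%
- Day 40: 39/84 = 46.4%
- Day 57: 56/84 = 66.7%
- Day 71: 70/84 = 83.3%

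Assume linear FVC change and k of 50 patients affected, with k from 1 to 5 (an assumed range). Shrinkage of the mean change = (k/50) x (1 - share):

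- Day 40: 0.02 x 0.536 = 1.1% (k = 1); 0.10 x 0.536 = 5.4% (k = 5)
- Extremes over Days 29 to 71: 0.02 x 0.167 = 0.3%; 0.10 x 0.667 = 6.7%

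**Step 6: size, cough.** Each affected patient is 1/50 = 2% of the sample and loses one of four primary values and one of three changes. At equal SD, the Week 12 interval widens by sqrt(50/49) - 1 = 1.0% for one patient and sqrt(50/45) - 1 = 5.4% for five.

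**The case against.** The strongest defence is that these cases are rare and of little consequence. In-office spirometry is scheduled only at V2 and V7, and no early-termination visit appears in the visible text, so an early last clinic FVC needs an unscheduled or brought-forward end-of-study visit. The cough case needs V6 completed and V7 never done in the clinic, although V6 comes only days before V7 and missed visits are referred for possible rescheduling. The study is exploratory, has no hypotheses, and lists all individual data. Parts of the SAP are not visible, and the visible text does not say which endpoints use observed cases and which use original results.

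All of this stands, and it limits the size of the effect. None of it supplies a rule that cures the table.

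A reader might also go further than the documents allow:

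- **That the stray recording has no window at all.** It has no V6 window. The V7 row, read literally, could capture it, so the assignment is ambiguous and the recording is not certainly lost.
- **That baseline FVC would be reused as Week 12, giving a change of zero.** With L = 1, Day 1 does fall in both rows. However, SAP 6.7, where it deals with a delayed baseline, applies the windows to subsequent visits. Reuse of baseline is therefore a strained reading, though worth excluding in words.
- **That the 70/71 mismatch matters.** A start day is printed, and Day 70 lies 10 days before the earliest protocol V6 (Day 80). It is clerical.

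**Conclusion.** The point holds as an edge-case rule error. Wherever the Table 6.7: 1 windows are applied, V7 accepts the last in-office visit on any day, early or late, as Week 12, and V6 excludes a completed recording that no clinic visit follows. Both follow from the printed cells.

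The effect is modest. It is nil for patients on schedule. Under the assumed 1 to 5 of 50 patients and linear FVC change, it is a 0.3% to 6.7% shrinkage of the mean Week 12 FVC change, or a 1.0% to 5.4% wider Week 12 cough interval. The true number affected cannot be derived from the documents. The reading of the table is secure; how far it reaches the primary endpoint depends on which endpoints use observed cases. The documents do not support a claim that the primary result is materially distorted. The correction is still worth making, because it is cheap and the present rule can put shorter or longer follow-up under a Week 12 label.

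**What to change.** 1. Define the V6 (Week 12) cough window by day, from its start day and with no reference to in-office attendance.
2. Prespecify lower and upper day limits for Week 12 FVC that contain the protocol's V7 window (Days 79 to 89, or 80 to 90 if counted after baseline). The lower limit could be the V6 start day. At Day 71 this leaves 79-71 = 8 days to spare and ensures that a Week 12 change covers at least 70/84 = 83% of the planned interval (69/84 = 82% if Day 70 is chosen). Report last in-office visits outside the limits as early or late end-of-study visits, not as Week 12.
3. State that the baseline measurement cannot also serve as Week 12.
4. As a clerical correction, reconcile the V6 offset (-13 gives 70) with the printed start day of 71.

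It would also help to state which endpoints use observed cases. The re-anchoring to the actual baseline date in SAP 6.7 can stay.

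**Cost.** SAP wording and programming only. A few more Week 12 FVC values will be missing. These come from early or late last visits and, because of re-anchoring, from some on-schedule V7 visits after a late in-office FVC baseline. With a lower limit of Day 71, a V7 on planned day 85 drops out once that baseline is more than 14 days late (85-14 = 71).
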